# 12. STATISTICAL METHODS AND SAMPLE SIZE DETERMINATION BY ASTRAZENECA

## **12.1** Description of analysis sets

## 12.1.1 Safety analysis set

The safety analysis set will be the Safety population, defined as all randomized patients who received at least 1 dose of study drug (12.5 mg NKTR-118, 25 mg NKTR-118, or placebo). The safety analysis set will be used to assess safety and tolerability variables.

## 12.1.2 Efficacy analysis set

The efficacy analysis set will be the modified Intent-to-Treat (ITT) population, defined as all randomized patients who received at least 1 dose of study drug (12.5 mg NKTR-118, 25 mg NKTR-118, or placebo) and have at least 1 post-baseline efficacy assessment.

## **12.2** Methods of statistical analyses

A comprehensive SAP will be finalized before unblinding of the data.

This is a general evaluation of long-term safety and evaluation. Therefore, no statistical testing will be conducted. Differences between NKTR-118 12.5 and 25 mg and placebo with respect to the evaluation of long-term safety and tolerability will be assessed using descriptive statistics.

The primary baseline will be defined as the latest non-missing value collected prior to the first dose of study drug in the previous pivotal study (D3820C00004) (screening, Visit 1 or Week 0, Visit 3), and a supportive baseline will be defined as the data collected at the final visit from the previous study (Visit 8). Where appropriate, to assess the potential impact of the previous 12 week treatment, the change from baseline in safety parameters will be summarized using both the primary (ie, prior to first dose of study drug in the previous pivotal study) and supportive (final visit of the previous pivotal study) baseline values.

The baseline data (including demographics, response to laxatives, medical history) for patients entering the study from a previous study will be pulled from the corresponding prior study databases and integrated with the data from this study in the analysis datasets. Additional medical history obtained during the previous studies (including adverse events ongoing at the end of the previous pivotal study) will also be reported.

Presentation of safety data will include summaries both by individual NKTR-randomized dose group (12.5 and 25 mg) as well as by a total NKTR group, where appropriate.

All major safety variables will also be presented by means of an outlier analysis. For labs, ECGs, and vital signs, these outlier criteria will be provided by the safety physician(s) and included in the SAP. For analyses such as modified Himmelsbach and NRS, generally accepted outlier criteria are not available but will be determined as appropriate before the time of database lock.

## 12.2.1 Safety analyses

Adverse events will be coded using the MedDRA dictionary. Three sets of AE summaries will be generated: (1) all AEs recorded in the clinical database, (2) all TEAEs (as defined in Section 11.1.1), and (3) AEs occurring after the last dose of study drug.

Number of events and proportions will be tabulated by preferred term and system organ class. An event that occurred 1 or more times on the date of or subsequent to first dose of study drug will contribute one observation to the numerator of the proportion. The denominator of the proportion will comprise all patients in the Safety population. Adverse events will also be summarized by intensity and separately, by causality (as determined by the investigator). Should a patient experience the same preferred term/system organ class within multiple intensity or causality categories, the patient's worst occurrence (most severe/most related) will be retained in the tabulations. Serious AEs and commonly occurring AEs will be summarized in a generally similar manner. Adverse events of special interest may be further summarized and analysis of AEs occurring within specific time periods (eg, after 1 month, after 3 months, etc.) may be considered.

Adverse events, SAEs, AEs leading to death, and AEs leading to study discontinuation will be tabulated for each treatment group. Descriptive statistics for time to onset and duration of select AEs may be summarized by treatment group. Adverse events that could potentially be indicative of centrally mediated opioid withdrawal, abuse potential, and bowel perforation will be identified prior to unblinding and will also be summarized by each treatment group.

The mean daily opioid dose will be summarized by treatment group for the following intervals: enrollment to Week 4 and Week 4 to Week 12, as well as randomization in the previous pivotal study (D3820C00004) to Weeks 4 and 12 in this study. The mean bisacodyl dose per week will be summarized by treatment group using descriptive statistics for the following intervals: enrollment to Week 4 and Week 4 to Week 12. The observed and change from baseline in composite modified Himmelsbach score will be summarized by treatment group at Week 12 using descriptive statistics. The observed score and change from baseline in NRS pain scores (average in the 7 days prior to the study visit) will be summarized by treatment group for Weeks 4, 8 and 12.

All laboratory test results, vital signs (sitting blood pressure and pulse), ECG results, body temperature, respiratory rate, and weight will be summarized for each treatment group using descriptive statistics at each visit for observed values and change from baseline.

The overall incidence, as well as shifts from baseline to each post-baseline visit, of potentially clinically significant laboratory test results, vital signs, ECG results, body temperature, respiratory rate, and weight will be summarized by treatment group. For visits where triplicate ECGs are obtained, the mean value of the 3 measurements will be used in the analysis.

Physical examination results (normal/abnormal by body system) will be summarized for each visit by treatment group. Changes from baseline in the physical examination results will be assessed using shift tables.

The proportion of patients with suicidal behavior and suicidal ideation throughout the study based on the C-SSRS will be presented for each treatment group. The proportion of patients within each of the 4 suicidal behavior categories and within each of the 5 suicidal ideation sub-categories will also be presented for each treatment group. Descriptive statistics on the total number of attempts, total number of interrupted attempts, and total number of aborted attempts will be summarized for each treatment group.

Total exposure to NKTR-118 12.5 and 25 mg will be summarized combining the data from the current study with the exposure data from the previous pivotal study (D3820C00004).

Safety parameters may also be summarized by age group, gender, race, region, and response to laxatives (LIR, non-LIR), as appropriate.

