- Use of concomitant medication (other than enema rescue medication or opioid medication) since Visit 3 will be recorded. (Note: use of bisacodyl will not be asked about and recorded, but will be determined by pill counts of returned bisacodyl and captured on the bisacodyl accountability eCRF).
- AEs since Visit 3 will be recorded.
- Modified Himmelsbach scale will be completed.
- Unused bisacodyl will be returned.
- Unused study drug will be returned and the number of unused study drug tablets will be recorded. Patient compliance will be determined.
- An appointment for Visit 5 (Final Visit, Day 99) will be made for patients who do not participate in the 52-week safety extension study.

Following Visit 4, patients may resume any constipation regimen that they and the investigator feel is appropriate, unless they choose to continue in the 52-week safety extension study. Note: Visit 5 is not required for patients who enter the 52-week safety extension study.

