### 6.3.4 Recording of adverse events

#### Time period for collection of adverse events

For patients who do not enroll in an extension study, all AEs will be collected from the time of signature of informed consent to the follow-up visit (Visit 5), whether or not related to the IP and must be recorded on the eCRF. Unsolicited reports of SAEs will also be collected for 30 days after the last dose of study drug.

For patients who enroll in an extension study, AEs and SAEs will be collected from the time of signature of informed consent to the last treatment visit (Visit 4), whether or not related to

the IP and must be recorded on the eCRF. Additional AE and SAE reporting will occur in the extension study.

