## **11.2** Calculation or derivation of safety variable(s)

## 11.2.1 Adverse events

A treatment-emergent adverse event (TEAE) is defined as any AE that started on or after the first dose of study drug up to the last dose of study drug. An AE already present at the time of the first dose of study drug that worsens in intensity following exposure to study drug or an AE with an unknown/not reported onset date will also be considered as treatment-emergent. Adverse events occurring after the last dose of study drug will also be summarized, which among other purposes, may assess any potential withdrawal-type effects.

Time to onset of an AE (in days) will be calculated as:

AE start date - Date of the first dose of study drug + 1.

Duration of an AE (in days) will be calculated as:

AE resolution date - AE start date + 1.

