## 12.2.2 Efficacy analyses

Descriptive statistics by treatment group for the PAC-SYM total score and each domain score will be summarized at baseline, Weeks 4, 12, and 14 as well as the change from baseline to each post-dose time point. Descriptive statistics by treatment group for the PAC-QOL total score and each domain score will be summarized at baseline, Weeks 4, 12, and 14 as well as the change from baseline to each post-dose time point.

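### Proportions of AEs after the last dose are divided by the whole Safety population, although patients entering the 52-week study have almost no off-treatment follow-up in this trial

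*Protocol*

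**What the plan says.** Protocol Section 12.2.1 lists three AE summaries: all AEs, treatment-emergent AEs, "and (3) AEs occurring after the last dose of study drug". The next paragraph sets how proportions are formed: "The denominator of the proportion will comprise all patients in the Safety population". No different denominator is given for the third summary. Section 12.1.1 says the Safety population is "defined as all randomized patients who received at least 1 dose of study drug", so follow-up after treatment is not a condition of membership.

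Section 11.2.1 gives a purpose for the third summary: "Adverse events occurring after the last dose of study drug will also be summarized, which among other purposes, may assess any potential withdrawal-type effects".

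Follow-up depends on what the patient does next. Under Section 6.3.4, patients who do not enter an extension have AEs collected to Visit 5, with unsolicited SAE reports to 30 days after the last dose. For those who do enter one, "AEs and SAEs will be collected from the time of signature of informed consent to the last treatment visit (Visit 4"), and later events are reported in the extension study. Section 3.1.2.2 adds: "Note: Visit 5 is not required for patients who enter the 52-week safety extension study". Footnote b of Table 1 repeats the exemption.

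**The concern.** A proportion of patients with an event should have in its denominator the patients in whom the event could have been observed. Here a group of unknown size is counted as event-free after treatment because this study stopped looking.

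The study compares arms descriptively and plans no testing (Sections 2.1 and 12.2), so the displayed proportions are themselves the result. No later model would correct the denominator. Little else in the study observes patients for withdrawal after stopping: the modified Himmelsbach scale is scored only at Visits 1 and 4, the NRS is not collected at Visit 5, and the opioid dose intervals end at Week 12. The treatment-emergent window closes at the last dose, so events that start later drop out of the second summary, and the first summary does not separate them. An understated third summary could make stopping look more benign than the data show.

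**Working it through.** The protocol states no rollover share, post-treatment AE rate or sample size target, so there is no figure to reproduce. The size is shown over assumed ranges.

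**Inputs**
- Maximum N: 630 (Section 3.1). Equal allocation to three arms is assumed, because this protocol does not state the ratio: 630 / 3 = 210 per arm.
- r = share of an arm entering the 52-week study (assumed).
- p = true proportion with an AE in the post-treatment period (assumed, and taken as the same in patients who do and do not roll over).

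**Formulas**
- As planned: events / Safety N = p × (1 − r).
- With followed patients only: events / (Safety N × (1 − r)) = p.

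**Dilution within one arm of 210**

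| r | Followed | Events at p = 10% | Planned, p = 10% | Planned, p = 5% |
|---|---|---|---|---|
| 20% | 168 | 16.8 | 8% | 4% |
| 40% | 126 | 12.6 | 6% | 3% |
| 50% | 105 | 10.5 | 5% | 2.5% |
| 60% | 84 | 8.4 | 4% | 2% |
| 80% | 42 | 4.2 | 2% | 1% |

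Dividing by the followed patients returns 10% (or 5%) in every row.

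**The short window for rollovers.** Section 3.1.1 has patients hold the Visit 4 morning dose, so about one day lies between the last dose and the end of AE collection. If events were spread evenly over the 14 days to Visit 5 (an assumption), rollovers would add about r × p / 14. At r = 50% and p = 10% that is 0.5 × 10% / 14 = 0.36 points, which moves the displayed 5% to about 5.4%. Events clustered on the first day would add more. The dilution is therefore roughly, not exactly, the rollover share. The figures below ignore this window.

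**Between arms**
- Equal rollover of 50%, true 15% on drug vs 10% on placebo: displayed 7.5% vs 5%. The ratio stays 1.5, but the difference shrinks from 5 to 2.5 points.
- Rollover 60% on drug vs 40% on placebo, true 10% in both: 10% × 0.4 = 4% vs 10% × 0.6 = 6%, an apparent ratio of 0.67.
- The same rollover, true 15% vs 10%: 15% × 0.4 = 6% vs 10% × 0.6 = 6%. The excess disappears.
- Rollover reversed (40% vs 60%), true 10% in both: 6% vs 4%, an apparent ratio of 1.5.

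**Precision.** At r = 50% and p = 10%, the planned figure is 5% of 210, with standard error √(0.05 × 0.95 / 210) = 1.5 points. The corrected figure is 10% of 105, with √(0.10 × 0.90 / 105) = 2.9 points. Relative to the estimate these are 0.30 and 0.29. The same 10.5 events carry the information either way, so the narrower absolute error under the plan is not a gain.

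**The case against.** The best defence is that the denominator sentence is a general rule never meant for the third summary. The sentence before it counts events on or after the first dose, which reads as an on-study incidence rule, and a statistical analysis plan is promised before unblinding. That plan could indeed set the right denominator. But an event after the last dose is also after the first dose, so the rule covers it literally. The protocol fixes the denominator here, and an analysis plan that followed it would carry the fault forward.

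It is also fair that this table is ancillary. Section 11.2.1 says only that it may assess withdrawal-type effects, as one purpose among others. Withdrawal on drug is addressed by the modified Himmelsbach scale, pain scores, opioid dose and a pre-specified set of AEs. Event counts are tabulated as well and do not depend on the denominator. These points limit the severity; they do not make the proportions right.

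Three stronger readings are tempting and not supported:
- **That rollovers cannot contribute any post-treatment event.** The held Visit 4 dose leaves about one day, and later events are reported in the extension study.
- **That the comparison between arms will be biased.** This needs unequal rollover. The documents give no rollover figures, and equal rollover preserves the ratio.
- **That the Week 14 summaries share the fault.** PAC-SYM and PAC-QOL ("summarized at baseline, Weeks 4, 12, and 14 as well as the change from baseline to each post-dose time point"), laboratory and ECG changes have no Safety-population denominator stated, so they are not diluted. They describe a selected group off drug, but the protocol labels that visit as follow-up two weeks after the last dose and plans no Week 12 to Week 14 contrast. Where those results are tabulated is a presentation choice.

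**Conclusion.** The point holds at moderate severity. Followed as written, Section 12.2.1 understates post-treatment AE proportions by roughly the rollover share whenever anyone enters the 52-week study. That direction follows from the protocol's own text. The size does not: it rests on assumed rollover and event rates, and on equal underlying risk in patients who do and do not roll over. Distortion between arms is possible but conditional on unequal rollover. The fault does not reach the treatment-emergent summary or any other planned analysis, and it does not affect data collection.

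**What to change.** Add one sentence to Section 12.2.1: for AEs after the last dose, the denominator is the Safety patients who did not enter the 52-week study and had follow-up after the last dose, and that N is shown by arm. Alternatively, give rates per patient-time of post-treatment follow-up, which also handles the short window in rollovers and unequal follow-up generally.

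State the limit beside the table. The change removes the dilution, but the patients who remain stopped early or declined the extension. They may differ from those who continued, and the mix may differ by arm, so the comparison is not protected by randomization. Showing the number followed next to the arm total lets the reader judge this.

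The cost is one sentence and a changed table shell, with a smaller N and a wider absolute margin on each proportion. No new data are needed.

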# 2. STUDY OBJECTIVES

# 2.1 **Primary objective**

The primary objective of this study is to compare NKTR-118 12.5 and 25 mg with placebo regarding long-term safety and tolerability in the treatment of OIC using descriptive statistics.

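### AE proportions use the whole Safety population while the TEAE window closes at last dose, and the only named exposure summary omits placebo and does not match the 12-week AE counts

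*Protocol*

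**What the plan says.** The primary objective (Section 2.1) is to "compare NKTR-118 12.5 and 25 mg with placebo regarding long-term safety and tolerability", by descriptive statistics alone. Section 12.2 confirms that nothing will be tested, so the AE tables carry the comparison.

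Section 12.2.1 sets both parts of the AE proportion. Numerator: "An event that occurred 1 or more times on the date of or subsequent to first dose of study drug will contribute one observation". Denominator: "The denominator of the proportion will comprise all patients in the Safety population". Three sets of AEs are summarised: all recorded AEs, TEAEs, and AEs after the last dose. A TEAE is "any AE that started on or after the first dose of study drug up to the last dose of study drug" (Section 11.2.1), plus pre-existing AEs that worsen and AEs of unknown onset.

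On exposure, Section 12.2.1 has one sentence: "Total exposure to NKTR-118 12.5 and 25 mg will be summarized combining the data from the current study with the exposure data" from the pivotal study. Placebo is not mentioned, nor is exposure within this study alone.

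Two analyses that take account of time are allowed but not promised: "analysis of AEs occurring within specific time periods (eg, after 1 month, after 3 months, etc.) may be considered", and time to onset of selected AEs may be summarised.

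**The concern.** The TEAE window shortens when a patient stops drug, but the denominator does not. Two arms with the same AE hazard and different drop-out will therefore show different crude TEAE proportions. Section 5.8 lists stopping reasons that could fall unevenly: inability to tolerate the assigned dose might fall more on active drug, and refractory worsening of constipation more on placebo. Discontinued patients are not replaced.

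A reader would normally judge this from time on drug by arm. The exposure summary as worded does not give it. It names no comparator, and it adds 12 weeks of pivotal-study treatment whose AEs are not counted here. At stake is how accurately the main safety comparison can be read, in a study whose purpose is that comparison.

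**Working it through.** **Do the exposure and the AE counts cover the same period?** AEs of this study are collected from consent at Visit 1 (Section 6.3.4). AEs still ongoing from the pivotal study are entered as medical history (Section 3.1.1). The AE counts thus cover the 12-week extension and any follow-up. The combined exposure covers up to 24 weeks. For a patient who completes both studies, time at risk for the counted TEAEs is 12 of 24 weeks, or 0.5 of the summarised exposure. Dividing these AE counts by that exposure would about halve the rate. The protocol does not plan that division, but it names no matching figure either.

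**How large can the crude distortion be?** The protocol states no AE incidence, drop-out rate or sample-size calculation (Section 12.3), so there is no figure to reproduce. The following is an illustration on assumed inputs.

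- p: 12-week AE incidence with no drop-out, 20% or 40% (assumed), the same in both arms.
- d: 12-week drop-out, 5% to 30% (assumed), independent of the AE counted.
- Constant hazards over 12 weeks: 12λ = −ln(1 − p) and 12μ = −ln(1 − d).

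Expected crude TEAE proportion = λ/(λ + μ) × [1 − (1 − p)(1 − d)].

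First-event rate = crude proportion ÷ mean time to first AE, drop-out or Week 12, which equals λ.

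For p = 0.40:

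- d = 0.10: 0.5108/(0.5108 + 0.1054) × (1 − 0.54) = 0.8290 × 0.46 = 38.1%
- d = 0.30: 0.5108/(0.5108 + 0.3567) × (1 − 0.42) = 0.5888 × 0.58 = 34.2%

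| Incidence p | Drop-out, lower vs higher arm | Crude proportions | Difference (points) | Ratio | Hazard ratio that would show as equal proportions |
|---|---|---|---|---|---|
| 20% | 5% vs 15% | 19.5% vs 18.5% | −1.0 | 0.95 | 1.06 |
| 20% | 10% vs 20% | 19.0% vs 18.0% | −1.0 | 0.95 | 1.06 |
| 20% | 10% vs 30% | 19.0% vs 16.9% | −2.1 | 0.89 | 1.14 |
| 40% | 5% vs 15% | 39.1% vs 37.2% | −1.9 | 0.95 | 1.07 |
| 40% | 10% vs 20% | 38.1% vs 36.2% | −1.9 | 0.95 | 1.07 |
| 40% | 10% vs 30% | 38.1% vs 34.2% | −4.0 | 0.90 | 1.16 |

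The last column is the true hazard ratio in the higher-drop-out arm that would be hidden completely. The first-event rate is the same in both arms of every row: 0.2231/12 × 52.18 = 0.97 per patient-year (97 per 100) at p = 20%, and 0.5108/12 × 52.18 = 2.22 (222 per 100) at p = 40%.

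In patients, with the maximum of 630 and equal arms assumed (630/3 = 210), the largest gap is 0.0398 × 210, or about 8. For a rarer event at 5% incidence, 10% vs 30% drop-out gives 4.7% vs 4.2%, about 1 patient per 210.

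**The case against.** The strongest reply is that crude incidence in the safety set is a conventional description, and that rates and exposure by arm are commonly left to the SAP, which Section 12.2 promises before unblinding and which is not at hand. Nothing in Section 12.2.1 forbids such tables. That stands as far as it goes. But the protocol does not leave the method blank: it fixes the denominator and words the exposure summary. It also commits to a per-patient-year rate, based on days on study drug, for healthcare visits by arm (Sections 11.6.2 and 12.2.3), an exploratory outcome, while naming no such rate for the primary safety outcome.

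Four stronger readings are tempting, and the documents do not support them.

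- A reader might infer that NKTR-118 will look safer than it is. No drop-out rates are given, and either arm may lose more. If placebo loses more through worsened constipation, NKTR-118 looks worse.
- A reader might take the Phase II discontinuations (Section 1.4) as evidence of unequal stopping. Of 12 for AEs, 10 were at 50 mg, a dose not studied here; 25 mg and 5 mg had 1 each. Entrants have also already completed the 12-week pivotal study (Section 4.1).
- A reader might think every stopper dilutes the proportion. A patient who stops because of an AE is already in the numerator for that AE. The dilution arises from loss unrelated to the AE being counted.
- A reader might conclude that crude proportions are all there is and that nothing could correct them. Section 12.2.1 also commits to event counts, all recorded AEs, AEs after last dose, and AEs leading to discontinuation by arm. Days on drug must be derived for every arm for the healthcare rate. An extension-only exposure summary is not named, but it is not excluded.

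**Conclusion.** The point holds as a modest improvement, not as an error that undermines the study. The committed TEAE proportion ignores time at risk, no person-time AE rate is committed, and the one named exposure summary neither covers placebo nor matches the AE counts. Under constant hazards and drop-out independent of the counted AE, gaps of 10 to 20 points distort the crude comparison by about 1 to 4 points at 20 to 40% incidence, and by less for rare events. Neither the size nor the direction in this trial can be settled from the protocol.

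**What to change.** In Section 12.2.1, keep the crude proportions and add two items.

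1. By arm, patients with a first event per 100 patient-years at risk, for TEAEs, SAEs, AEs leading to discontinuation and the safety topics of interest. For on-treatment events, time at risk runs from first dose in this study to the first event or the last dose.
2. Exposure during this study for all three arms, placebo included, shown separately from the combined 24-week exposure.

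No new data are needed: AE start dates are collected (Section 6.3.4), time to onset is defined (Section 11.2.1), and days on study drug are already required (Section 11.6.2). The cost is extra table columns. The rate assumes a roughly constant hazard and treats stopping as unrelated to the event, so it should be read alongside the proportions, not in place of them.
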